**IV. Preliminary Studies:**

Our preliminary studies, including a national study of care management in Aetna and implementation of a cross-diagnosis CCM across the National Network of Depression Centers demonstrate our collective expertise in development and implementation of mood disorder CCMs to improve outcomes across a wide variety of practices, and support the readiness of the mood CCM for a plan-level RCT.

**C.1. Mood disorders in Aetna: Identifying and addressing the need in solo/small practices.** Aetna Inc. is the fifth largest healthcare insurer in the country, providing benefits through employers in all 50 states, with products and services targeted specifically to small, mid-sized and large multi-site national employers. Aetna Behavioral Health serves approximately 12 million covered lives, with 244,971 providers across 157,523 practices filing claims in the past year. Thus while this specific RCT is sited in a single health plan, Aetna has the size and diversity sufficient to represent a wide range of commercially funded care for mood disorders in the US. Aetna has had a longstanding and stable commitment to implementing disease management for high-prevalence, high-cost mental health conditions, as well as a track record of NIH-funded research (e.g.,

1R01DA029716; 1R01DA026414). Aetna’s commitment to sustaining and expanding mental health care management—and the mood disorders CCM in particular—is underscored in the letters from both [name] and Aetna’s in-kind contribution outlined in the Budget Justification.

**C.2. Most Aetna beneficiaries receive care for bipolar disorder from small or solo practices.** Using all Aetna Behavioral Health claims data from 2009, we determined practice size based on number of participating providers linked to the same tax identification number. Unlike the situation for primary care and multi-specialty groups (19, 20, 91), care for bipolar disorder is predominantly provided in small behavioral health practices, with the vast majority of individuals with bipolar disorder treated in solo practices (Table 1). Further, among Aetna patients with bipolar disorder from solo or small practices, **23% (N=2785) were hospitalized** in the past year. This distribution convinced us that it is critical to focus the study on smaller or solo practices in order to truly reach a vulnerable population who to date may not have access to effective care management.

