**Patient-level secondary outcomes** include guideline-concordant (quality of) care, hospitalizations, as well as self-reported productivity. These measures are based on recommended indicators from the Accountable Care Organization published rules for performance measures and shared savings (111). We will apply previously established quality measures for mood disorders (98, 111, 112), and cardiometabolic management (113, 114) (Table 5). Quality of care data will be gathered from electronic medical records (eTUMS) and **hospitalization data** will be ascertained from Aetna utilization and claims files at the end of patients' 12 and 24-month participation in two prospectively observed 6-month intervals. Preventable hospitalizations over the 12 and 24-month period will be defined using the AHRQ Ambulatory Care Sensitive Condition (ACSC) definition (115), which identifies conditions for which "good" outpatient care can potentially prevent the need for hospitalization or for which early intervention can prevent complications or more severe disease. We will also assess the probability of psychiatric rehospitalization separately. **Patient-level productivity** over the 24-month period will be assessed in the survey using the Work Limitation Questionnaire(116).

**Patient factors** include CCM engagement ascertained from the patient survey. Engagement is based on the six-item Preference Index for Decision-Making (**API-D**; (117, 118)) which has been used in chronically ill samples to investigate the desire for collaborative care from clinicians. Other patient factors include demographic and clinical information, including co-occurring symptoms (substance use (121, 122), comorbidities (from eTUMS).

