**Aim 3: Utilization, costs, CEA, and business case:** Primary utilization measures of interest, including outpatient services, inpatient (including length of stay), and ER use, and health care costs will be ascertained from Aetna eTUMS electronic record reviews using a standard assessment tool (125). Cost data will be estimated for each inpatient, ER, and outpatient visit using Current Procedural Terminology (CPT) codes. A relative value unit (RVU) weight will allow for the use of the Medicare Fee Schedule to calculate a standardized cost for each service. Costs incurred in different years will be discounted at an annual rate of 3% and adjusted for inflation and discounted to the baseline (first) year of the study. Other costs incurred by the participants including medications, visit co-pays, transportation, and time involved in the CCM will be ascertained from the

patient survey. CCM cost data will be estimated using a time-motion survey developed by study investigators (R01 MH 79994) administered monthly to the CMs and quarterly to providers over a 2-year period, which ascertains time spent on CCM activities, including self-management, phone contacts, and documentation.

**C.5.g. Analyses.** General approach: The principal analyses will be for the primary hypotheses. An intent-to-treat analysis will be performed for all analyses. Bivariate baseline analyses will first be conducted to see if randomization was successful by comparing patient demographics and clinical characteristics (e.g., mental health diagnoses) between randomization groups. If there is a lack of equal distribution across groups, these variables will be added as covariates to analyses or propensity scoring will be used. Baseline characteristics will be compared among those enrolled but dropped out over time to those who remained in the study. Our unit of analysis for patient-level outcomes will be patients nested within practices with an indicator for non-solo practice provider sites (126, 127) and an indicator for patients diagnosis (bipolar vs. unipolar depression).

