Missing Data: We attained subject retention of 80% over a three-year follow-up in one study (50, 51), and recent 1-year data (MH0745409) indicate 90% retention. Extent and pattern of missingness will be examined for outcome variables as well as for baseline covariates. We expect missingness to be completely at random or at random, in which case the proposed analytical methods will give unbiased estimates of treatment comparison. We will examine how sensitive our conclusions are to potential non-ignorable missingness using a pattern mixture model that will allow us to either model the observed pattern of missingness or change the imputations to represent the likely differences in conditional distributions between observed and missing data (128, 129). For the latter, we will combine the results from each imputed data using Rubin's rules (130).

**Aim 1 primary outcomes (H1a: symptoms, quality of life):** Primary outcomes are continuous, and based on pilot data, are expected to be normally distributed. If a continuous outcome exhibits a significant lack of normality, other options will be considered including data transformation, categorization, and non-parametric analyses. Four linear mixed-effects models accounting for clustering will be run to assess the CCM effects compared to EC on changes in PHQ-9, ISS, and SF-12 PCS and MCS scores over 12-months, adding baseline values of the outcome measure, the effect of CCM, time, and CCM X time interaction.

**Aim 1 secondary analyses:** For guideline concordance and hospitalization, we will compare the likelihood of receiving the guideline-concordant treatment over 12 months (Table 5) as well as the likelihood of an ambulatory care sensitive admission using a generalized linear mixed-effects model (GLM) with logit link. Similar to our primary hypotheses, linear mixed-effects models will be conducted to determine the effect of CCM vs. EC on changes in the Work and Social Adjustment Scale.

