bootstrapping approach will be employed. For the business case, additional analyses will be conducted in which changes over time in utilization and costs of inpatient, ER, and outpatient services (medical, psychiatric) will be compared between patients in the CCM or EC arms over a 2-year period, in order to determine the time dynamics by which the CCM led to changes in health care costs. Additional cost analyses will take into consideration the return-on-investment of the CCM and changes in enrollee turnover (134).

**C.5.h. Business plan development (Aim 3).** The business case development plan is based on our Enhanced REP framework (73) and informed by the work by Leatherman and colleagues (also see Appendix for submitted paper on business case). In brief, a business case for the CCM exists if the Aetna realizes a financial return on investment or other positive impact on organizational function or sustainability within a “reasonable” time frame (134). Other positive impacts beyond the potential cost savings from implementing CCM include revenue-based from the payer perspective (i.e., value added to payers when the health plan offers CCMs in terms of improved enrollee health and access to care). We chose 2 years as the time frame for outcomes in this study because prior research on CCMs has not found a return-on-investment within one year (3), and 2 years is below the average tenure of an Aetna enrollee. From a business case standpoint, attrition from the health plan may attenuate savings from the initial investment, and our analysis will implicitly account for this by only counting within-plan utilization costs. Enhanced REP addresses organizational and financial incentives (Table 6) designed to inform the CCM return-on-investment (73) and will lead to the development of a reimbursement model for CCMs. Preliminary stages for business case development (134), including (a) the implementation of a program (CCM) shown to improve patient health (135), (b) establishment of quality and cost indicators aligned with existing national initiatives (e.g., ACOs), and (c) identification of a health plan champion and consultant team have been completed. The remaining years (3-5) will be devoted to refining and marketing the business plan, which will include a CCM reimbursement strategy.

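### The claims-based Aim 1 secondary outcomes have no rule for time after a patient loses Aetna coverage, and the yes/no logit model has no place for unequal observed time

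*Combined protocol and SAP*

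**What the plan says.** Section II makes guideline-concordant care and hospitalizations secondary hypotheses of Aim 1. Table 5 and C.5.f take both from Aetna's care-management record (eTUMS) or claims.

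- **Model.** C.5.g (Aim 1 secondary analyses) states "we will compare the likelihood of receiving the guideline-concordant treatment over 12 months (Table 5" and adds "the likelihood of an ambulatory care sensitive admission using a generalized linear mixed-effects model (GLM) with logit link". C.5.f says of readmission: "We will also assess the probability of psychiatric rehospitalization separately". No model is named for that outcome.
- **Windows.** Table 5 scores mood treatment over a 6-month period. C.5.f gathers hospitalization data "at the end of patients' 12 and 24-month participation in two prospectively observed 6-month intervals" and defines preventable admissions over both 12 and 24 months.
- **Population.** C.5.g: "An intent-to-treat analysis will be performed for all analyses".
- **Coverage.** C.5.b requires current Aetna coverage of at least 6 months at entry. Nothing is said about coverage after randomization.
- **Leaving the plan.** C.5.h recognises that "attrition from the health plan may attenuate savings from the initial investment" and deals with it by counting only costs incurred within the plan. C.5.h and the Aim 3 analysis text are the only places where leaving the plan is mentioned.
- **Missing data.** C.5.g examines missingness of outcome variables in general and states: "We expect missingness to be completely at random or at random, in which case the proposed analytical methods will give unbiased estimates of treatment comparison". A pattern-mixture sensitivity analysis with imputation is planned.

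**The concern.** A survey that is not returned leaves a visible gap. A claims file does not: after coverage ends, an admission, prescription fill or laboratory test produces no Aetna record, and the absence looks the same as a true 'no'. Unless someone defines uncovered time as missing or censored, the missing-data plan has nothing to act on for these outcomes, while intent-to-treat keeps every patient in the denominator. A logit model of a period-long yes/no cannot tell a patient observed for 3 months from one observed for 12.

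The misreading affects leavers who had no recorded event before leaving. A patient with an admission or qualifying treatment already on record is correctly a 'yes'.

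Loss of coverage could well be related to illness. C.1 describes Aetna as "providing benefits through employers in all 50 states", and every participant has had a recent psychiatric hospitalization, so job loss is one possible route out of the plan. The documents do not quantify this. At stake are a diluted concordance effect if the arms lose coverage equally, and a false arm difference on two secondary hypotheses if they do not. A missing 'yes' reads as worse care for concordance but as fewer admissions for hospitalization, so the same loss pushes the two hypotheses in opposite directions of apparent benefit.

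**Working it through.** **Inputs from the documents.** Concordance 46.5% (CCM) and 27.1% (EC), 172 patients per arm, ICC 0.05, 2 patients per practice, two-sided 0.05 test (all C.5.i). A 23% past-year hospitalization proportion among bipolar patients in solo or small practices (C.2), used only as an illustrative admission risk. **Assumed:** exit rates of 10%, 20% and 30% by month 12, because none is given.

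**Step 1. The plan's own figure.** Design effect 1 + (2 − 1) × 0.05 = 1.05, so effective n = 172/1.05 = 163.8 per arm. The two-proportion test with pooled null variance gives 95.7% power for 46.5% vs 27.1%. After 20% loss (137.6 per arm, effective 131.0) it gives 90.7%. The stated power of more than 90% is reproduced.

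**Step 2. Recorded risk if leavers without an event read 'no'.** Let p be the true 12-month risk, h = −ln(1 − p), and let exits fall evenly over the year with a constant hazard. A leaver's mean recorded risk is m = 1 − p/h. With exit share e, recorded risk = (1 − e)p + e·m.

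- p = 0.465: h = 0.6255, m = 0.2566
- p = 0.271: h = 0.3161, m = 0.1426
- p = 0.23: h = 0.2614, m = 0.1200

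**Step 3. Equal exit, concordance.** At e = 0.20, CCM is 0.8 × 0.465 + 0.2 × 0.2566 = 42.3% and EC is 0.8 × 0.271 + 0.2 × 0.1426 = 24.5%, a difference of 17.8 points. The worst case, every leaver 'no', is 19.4 × (1 − e).

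| Exit, both arms | Difference, even exit | Power | Difference, every leaver 'no' | Power | Leavers set to missing: power (19.4 kept) |
|---|---|---|---|---|---|
| 10% | 18.6 | 94% | 17.5 | 92% | 94% |
| 20% | 17.8 | 93% | 15.5 | 87% | 91% |
| 30% | 17.0 | 91% | 13.6 | 81% | 87% |

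The last column drops leavers entirely and assumes that leaving is unrelated to outcome.

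**Step 4. Unequal exit, no true effect on admission (p = 0.23 in both arms).**

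- Exit 10% (CCM) vs 20% (EC): 0.9 × 0.23 + 0.1 × 0.1200 = 21.9%, and 0.8 × 0.23 + 0.2 × 0.1200 = 20.8%. The false CCM excess is 1.1 points, against a standard error of about 4.5 points; type I error is about 5.7%.
- Exit 10% vs 30%: 21.9% vs 19.7%, a false excess of 2.2 points; type I error is about 7.8%.
- If the exit rates are swapped between arms, the sign reverses.

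**Step 5. Unequal exit, no true effect on concordance, exit 10% vs 20%.** If every leaver reads 'no', the false difference is 0.1 × 27.1 = 2.7 points or 0.1 × 46.5 = 4.7 points, with type I error about 9% or 14%. If leavers lose half their chance of a 'yes', it is about 6% or 7%.

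**The case against.** Three stronger readings are tempting, and the documents do not support them.

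- *A reader might infer that the plan counts leavers as 'no'.* No section says so. The missing-data paragraph covers outcome variables without restricting itself to survey measures, so it could apply if uncovered time were defined as missing. What can be shown is that no such definition is given and that the default of a claims extract is 'no'.
- *A reader might infer that all these outcomes rest on a fixed 12-month window.* The 12-month phrase in C.5.g is attached to guideline treatment. Table 5 and C.5.f also use 6-month windows, and 24 months for preventable admissions. The windows are not reconciled, and shorter ones do not help unless each has a coverage rule.
- *A reader might infer that the gap favours CCM.* Direction depends on which arm loses more coverage, and nothing in the documents suggests a difference.

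Other points on that side stand. The sizes are modest: under even, equal exit up to 30%, concordance power stays above 90%, and equal exit creates no false admission difference. C.5.h puts average tenure above 2 years, although that does not give the share leaving by month 12. The 23% figure is neither an ACSC rate nor a readmission rate in recently discharged patients; a lower risk would give a smaller artefact. Concordance is a measure met or not met in a period, so the constant-hazard model is only a rough guide for it. Family members can enrol, and a dependant's own job loss need not end coverage. Finally, if leaving is related to illness, censoring at coverage loss does not by itself remove the bias.

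**Conclusion.** The concern holds as an omission, together with a model that does not fit the data source. The plan draws three secondary outcomes from insurer records, secures coverage only at entry, expects people to leave, and deals with leaving only for costs. As written, the logit analysis cannot reflect unequal observed time, and the coding of uncovered time is left to whoever builds the dataset.

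With equal leaving the effect is dilution of the concordance difference, from 19.4 to 17.8 points at 20% exit, or 15.5 in the worst case (power 87%). A false difference needs exit to differ by arm. It is then 1.1 points for admissions at 10% vs 20% exit and a 23% risk, in a direction set by which arm loses more. Every exit rate here is an assumption. The case for change rests on a defined outcome and an unbiased comparison rather than on power: setting leavers to missing costs about as much power as mild dilution does.

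PHQ-9, ISS, SF-12 and the productivity measure come from the patient survey and are untouched. This should be corrected, but it does not threaten the primary analysis.

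**What to change.** 1. Export Aetna coverage start and stop dates with the claims, and define covered time for each patient.
2. Analyse ACSC admission and psychiatric rehospitalization as time to first admission, censored at loss of coverage. Alternatively, keep the yes/no outcome with a complementary log-log link and log covered time as an offset. Name the model for rehospitalization.
3. Score guideline concordance in the 6-month windows of Table 5 and C.5.f, and state how they combine into the 12-month comparison. Set any window without full coverage to missing whatever was recorded in it, because keeping only the recorded 'yes' values would bias the rate upward. The mixed model and the pattern-mixture sensitivity analysis of C.5.g then apply.
4. Report loss of coverage by arm, with timing.
5. Extend the sensitivity analysis to coverage loss, because the censored analysis assumes that leaving is non-informative given covariates and the window analysis assumes missingness at random.

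The cost is SAP wording, two date fields from the plan's membership file, and one added sensitivity analysis. The downsides are fewer scorable patient-windows for concordance and the assumptions named in item 5. The rule should be fixed before anyone sees outcomes by arm.

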### **Our Specific Aims are to:**

1. Determine whether individuals with mood disorders treated with a health plan-level CCM demonstrate improved health outcomes and quality of care at 12 months compared to those who are mailed educational material alone (Educational Control-EC).

Our **primary hypothesis** is that compared to EC, the mood CCM will result in a) reduced mood symptoms in 12 months, or b) improved health-related quality of life.

Our secondary hypotheses is that patients receiving CCM vs. EC will have improved guideline-concordant care (e.g., mood disorders treatment, cardiometabolic monitoring), reduced hospitalizations, and improved work productivity within 12 months.

2. To support subsequent CCM dissemination by identifying key organizational, provider, and patient characteristics associated with CCM engagement and outcomes.
3. To conduct a cost-effectiveness analysis of CCM versus EC on changes in patient utilities over 24 months and apply findings to develop a business case for CCMs in smaller practices.

This proposed R18 addresses **AHRQ's research demonstration and dissemination priorities**, particularly around prevention and care management, with an emphasis on vulnerable groups including more rural populations (the majority of Aetna enrollees are seen in smaller practices). It also confronts unanswered organizational and financial questions raised by a recent **AHRQ report** ("A National Agenda for Research on Collaborative Care"). As one of the first cross-diagnosis CCM-based implementation studies focused on small practices, this groundbreaking study is informed by an extensive partnership with a network-model health plan (Aetna). The study also applies a novel implementation framework (REP) in which the CCM is delivered by existing providers. In addition to the specific importance of this practice-research partnership to further implement CCMs among small practices at the health plan level within a natural experiment setting, this study will contribute to the evolution of the business case for CCMs in general, enhance the utility of plan-level panel management focused on vulnerable populations across different treatment settings, and inform remote technologies that will facilitate emerging healthcare initiatives (e.g., accountable care organizations, health IT).

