**Training** for care managers will follow existing Aetna standard procedures for telephonic and web-based training. This will consist of 16 hours of telephonic training by [name] and her study team over 2 weeks modeled after our current on-site training package.

**Technical assistance** will be provided by the Joint Operating Committee and supported by study consultants [name] (telephonic care management) and [name] (implementation processes). Joint Operating Committee members will conduct conference calls with the care managers (weekly) and supervisors (monthly) to guide the use of CCM components, particularly with regard to interface issues between: care managers and patients; care manager and providers/practices; and patients and providers. The Joint Operating Committee will have separate quarterly and ad hoc calls with consultants for debriefing and advice.

**C.5.f. Data Collection and Measures.** Key outcomes data will be ascertained from patients (including surveys, medical record- eTUMS reviews, and claims data) and organizational surveys (Table 5).

**Patient survey:** A concise (15-30 minute) quantitative survey will be collected from patients via phone at baseline, 6, 12, 18, and 24 months thereafter by the research associate (RA). If the RA is unable to reach the patient via phone for follow-up assessments after multiple attempts, a survey will be mailed to the confirmed last known address of the participant as a final attempt to receive this data. Patients will be asked to return this survey without any identifying information on the survey or the envelope. The survey will contain a subject ID number to identify the patient’s survey when it is returned via mail. Patient outcomes data will be entered by the RA into a database on a password-protected research computer within a secure network server at the University of Michigan.

**Patient utilization and cost data,** described below will be ascertained from the Aetna eTUMS and claims databases, and exported securely for merging with survey data and analysis at the University of Michigan.

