**Aim 2 analyses are considered exploratory** but will be used to gain insight into the mechanisms by which CCM impacts patient outcomes. We will first explore the strength and direction of the association between patient-level CCM engagement (API-D scores- see section C.5.f) (119) on changes in outcomes (SF-12, PHQ-9 and ISS scores) by adding patient-level API-D scores to the aforementioned linear mixed-effects models from Aim 1. We will also be run exploratory analyses in which we add key organizational factors (e.g., non-solo practice, practice type-primary care vs. behavioral health, presence of non-MD clinical staff, EMR use, ownership), and other patient factors (e.g., demographics, comorbidities) in the models specified in Aim 1. In secondary analyses we will also incorporate the number of additional optional sessions covering supplemental modules completed by the patient (Section C.5.d).

**Aim 3: Both a payer and societal-based cost-effectiveness analysis (CEA) will be conducted.** A CEA from the payer perspective will involve comparison of utilization costs of health service providers including CM's time ascertained from time-motion survey. A societal perspective will add non-health care costs incurred by patients including time and transportation. Generalized Linear Models with log link functions will be used to correct for heteroscedasticity and reduce the impact of outliers (131). The incremental effectiveness of CCM compared to EC will be measured by changes in health utilities, assessed using a method described by Zivin (132) and Brazier (133) which translates six of the SF-12 items to changes in health utility (SF-6) based on responses to standard gamble questions given by community members regarding all combinations of possible health states. Cost-effectiveness ratios will be calculated based on the difference in per patient costs and effectiveness of CCM versus EC. To quantify uncertainty around these ratios, a standard nonparametric

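### The Aim 3 cost-effectiveness ratio sets two years of costs against a utility change with no stated visit or time-integrated summary; 24-month QALYs from the planned surveys would settle it

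*Combined protocol and SAP*

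**What the plan says.** Effect measure. Under Aim 3 in C.5.g, "The incremental effectiveness of CCM compared to EC will be measured by changes in health utilities". The utility is the SF-6, derived from six SF-12 items. The ratio is then defined: "Cost-effectiveness ratios will be calculated based on the difference in per patient costs and effectiveness of CCM versus EC". Section II frames the aim as follows: "To conduct a cost-effectiveness analysis of CCM versus EC on changes in patient utilities over 24 months".

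Costs. C.5.f states "Costs incurred in different years will be discounted at an annual rate of 3" per cent, with care-management time surveyed over two years. C.5.h adds "We chose 2 years as the time frame for outcomes in this study". The Aim 3 paragraph of C.5.g does not repeat the cost horizon; 24 months is inferred from these places.

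Data available. Table 5 gives the patient survey as the source of the utilities, and C.5.f schedules that survey "via phone at baseline, 6, 12, 18, and 24 months thereafter".

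What is absent. No section mentions QALYs, an area under the curve, time-weighting or discounting of effects, and none says which visit or summary defines the change.

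**The concern.** The numerator of the ratio is a sum over time. The denominator, as worded, is a change on the utility scale with no duration attached. Two patients with the same utility at month 24 can have spent very different lengths of time in better health, and a change between two visits cannot tell them apart.

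The design makes timing relevant. The intervention lasts one year and is front-loaded, with ten weekly sessions plus monthly calls, so the 18- and 24-month surveys fall after it ends. In the pilot (Table 3), mean well-being rose 7.4 points with CCM (13.0 to 20.4) and 2.2 with control (10.2 to 12.4) by 6 months. That is a different scale and says nothing beyond 6 months, but it makes an early gain plausible and leaves its persistence open.

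At stake are the meaning of the ratio, its comparability with other programmes, and the freedom to choose the visit or summary once the data have been seen.

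**Working it through.** The documents give no expected utility difference, cost difference or ratio, so there is no planned figure to reproduce. The check asks how far different readings of the same wording can diverge.

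**Inputs.** Survey times of 0, 0.5, 1, 1.5 and 2 years come from C.5.f. The between-arm utility gains d6, d12, d18 and d24 are assumptions, with d0 = 0. So is the $1,000 cost difference.

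**Formulas.**
- Baseline-to-24-month change = d24.
- Trapezoidal area (QALYs) = 0.5 × [(0 + d6)/2 + (d6 + d12)/2 + (d12 + d18)/2 + (d18 + d24)/2] = 0.5 × (d6 + d12 + d18 + d24/2).
- Mean of the four follow-up changes, carried over two years = 2 × (d6 + d12 + d18 + d24)/4.

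**Worked case, fading benefit.** Area = 0.5 × (.04 + .04 + .02 + 0) = .050. The 24-month change is 0. The mean is .10/4 = .025, and over two years .050.

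| Assumed gain at 6/12/18/24 months | 24-month change | Area (QALY) | Mean change × 2 years |
|---|---|---|---|
| .04/.04/.02/0 | 0 | .050 | .050 |
| .04/.04/.02/.01 | .010 | .0525 | .055 |
| .04/.04/.04/.04 | .040 | .070 | .080 |
| .01/.02/.03/.04 | .040 | .040 | .050 |
| 0/0/0/.04 | .040 | .010 | .020 |

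**Reading the table.**
- The last three rows share one 24-month change, so an assumed $1,000 gives 1,000/.04 = $25,000 per utility point in each. Per QALY they differ: 1,000/.070 = $14,286, 1,000/.040 = $25,000 and 1,000/.010 = $100,000. The spread in area is .070/.010 = 7-fold. All figures scale with the assumed gain, so the 7-fold spread is the same at a gain of .02 (.035 against .005) or .08 (.14 against .02).
- In the first row the change-score ratio is undefined although there is benefit.
- The linear rise shows no numerical gap between change and area.
- The two-year mean exceeds the area by d24/4: nothing in the first row, .0025 in the second and .010 in the last three.

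**Discounting effects.** In the fading case, year 1 contributes 0.5 × (.02 + .04) = .030 and year 2 contributes 0.5 × (.03 + .01) = .020. Discounting year 2 at 3% gives .030 + .020/1.03 = .0494, a fall of about 1%. Across the profiles examined the fall is about 1–3%, so the missing rule for effects is a small matter beside the choice of summary.

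**The case against.** A reader might infer that the plan has chosen a start-to-end change and that its ratio will therefore be several-fold wrong or undefined. The documents do not support that. No section says baseline to 24 months. For Aim 1, C.5.g uses similar wording about changes over a period for mixed models with time and treatment-by-time terms, so a repeated-measures or averaged change is an equally natural reading here. On an averaged reading the fading case agrees with the area exactly. The trajectories are assumed, and nothing in the documents shows that utility gains fade. Dollars per utility point and dollars per QALY are also different quantities, so a gap between them is not an error in either. All of this stands.

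A reader might also infer that the business case requires cost per QALY. C.5.h defines it by return on investment or other benefit to the organisation, with separate two-year cost and utilisation analyses. That stands too, although Table 6 does name the cost-effectiveness analysis as an input to the business plan.

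Finally, C.5.j calls this analysis exploratory and not fully powered, Aim 1 is untouched, and the utilities are collected in any case. This limits the importance of the point. It does not supply the missing definition: the admissible readings still give different ratios, and none short of an area gives QALYs.

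**Conclusion.** The point holds as an undefined effect measure, not as a demonstrated error in the ratio. The plan specifies a change in utility without a visit or a time-integrated summary and sets it against costs accumulated and discounted over two years.

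The size is conditional on both the reading and the trajectory. With a baseline-to-24-month change, it ranges from no numerical discrepancy (linear rise) to an undefined ratio despite .050 QALY gained (fading benefit). With an averaged change, the discrepancy vanishes in the fading case and is otherwise a quarter of the 24-month difference. These figures rest on assumed utility gains and an assumed $1,000, and the 24-month cost horizon is inferred.

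What does not depend on the trajectory is the unit: on any of these readings short of an area, the result is cost per utility point, which limits comparison with other programmes. Because the analysis is exploratory but feeds the business plan, this is a cheap and worthwhile improvement, not a threat to the trial's main conclusions.

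**What to change.** In the Aim 3 paragraph of C.5.g, define effectiveness as QALYs over 24 months, calculated for each patient by the trapezoid rule from the SF-6 utilities at baseline, 6, 12, 18 and 24 months. State that:
- the between-arm difference is adjusted by regression for baseline utility;
- QALYs are discounted at 3%, as costs are;
- costs are counted over the same 24 months;
- each patient's costs and QALYs are resampled together in the bootstrap already planned.

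The cost is a few sentences and simple code, with no new data collection. The downside is that missed intermediate surveys must be imputed. C.5.g already describes imputation combined by Rubin's rules as part of its sensitivity analysis for missing data, and the text should say how imputation applies to the utilities.
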